9.2 Data Collection and Management

Data collected as part of this study will be managed in strict accordance with CHOP's secure confidentiality standards. Importantly, after consenting to participate, all participants will be assigned a unique, study-specific alphanumeric identifier (subject ID). This subject ID will be used to track all study data; although study staff will necessarily have access to identifiable participant information in order to contact participants and schedule visits, in no case will the

participant's name or other identifying information appear with study data. We will keep a master list containing identifying information and subject ID number in a secure encrypted database (REDcap), separate from coded data forms, so that name-to-alphanumeric ID code correspondence cannot be deduced. Identifying information, including consent forms and information sent to us by participants or families, will be kept in a separate secure locked file only accessible to study staff.

Online Data Collection: Online data collection will be facilitated by the Clinical and Translational Core (CTC) of the CHOP/Penn IDDRC. The Core is comprised of CHOP staff only; no Penn staff are involved in data collection or management. The CTC has negotiated contracts with publishers to allow the online administration of various questionnaires, and has standardized the data collection tools. In return for these services, the de-identified data collected using CTC services will be stored in a registry, if participants agree to the future use of their data.

Data Management. REDcap is a secure, password protected, encrypted web-based survey system based on a dedicated CHOP Research Information Systems server, and will be our primary tabular data management tool. Online questionnaires will be completed using REDcap, which will also store participants' behavioral and clinical data coded by a unique alphanumeric identifier (subject ID) assigned after consenting to participate. Study staff at CHOP will be able to log in to REDcap via a separate interface that allows them to manually enter or update data. Data exported by CAR researchers for analysis will be blinded of all personally identifiable information (associated only with subject ID). A built-in audit trail records the identity of individuals that access and/or change data in the system. Data are backed up to time-stamped files daily by CHOP Research Information Systems using automated backup routines. Backup files are encrypted and transferred to a secure file server accessible only to designated personnel. In the event of data error, loss or corruption, research personnel will work with CHOP Research Information Systems to determine the most appropriate recovery strategy. As part of consent, participants will be asked if their coded data can be used in future studies, or for this study only, for which it will be retained indefinitely. Identifiable information will be retained if permission is given to re-contact the participant or family for future studies. Any identifiable information that is obtained will remain confidential per the protocol's data management plan and will be disclosed only with participant/parental permission or as required by US or State law.

Data Analysis. Primary tabular data analysis will be conducted on secure CHOP-imaged computers, and will not include personally identifiable information about participants. All data collected as part of this study will be analyzed at the group level; subjects will be identified only by ID number to protect their confidentiality. Primary data analysis will be conducted on secure CHOP-imaged computers, and will not include personally identifiable information about participants.

9.3 Confidentiality

All data and records generated during this study will be kept confidential in accordance with Institutional policies and HIPAA on subject privacy. The Investigator and other site personnel will not use such data and records for any purpose other than conducting the study.

9.4 Regulatory and Ethical Considerations

9.4.1 Data and Safety Monitoring Plan

The PI will periodically review the data collection and storage practices associated with this study and determine whether changes to enhance confidentiality and privacy are required. The PI will frequently monitor the quality control of the data with staff and research assistants. Quality assurance will be monitored by the PI. Compliance with the monitoring plan and requirements for reporting will be ensured through signed documentation acknowledging confidentiality and human subjects safeguards.

This study will indirectly investigate adverse effects related to use of VR technology. The project team will attempt to minimize these effects by familiarizing participants with the personnel and setting at each site, and closely monitoring them during the study. Tests are administered by well-trained and supervised personnel and participants are debriefed after each session. There may be discomfort associated with participation, but in our experience subjects who are well informed on the purpose of the study and who are accompanied throughout the procedures by a member of the research team tolerate this discomfort well and without complications. One approach the study team will take to protect against risks associated with VR use is to limit the duration of consecutive time participants spend in VR trials. Each participant will take a break in between each VR trial. If a participant who had not previously experienced adverse effects subsequently experiences an adverse effect, research staff will follow up with the participant or a caregiver in regard to any change in the participant's medication regimen that might potentially impact tolerance of VR. A decision will then be made regarding ongoing participation in the study.

A Data and Safety Monitoring Board will be established for this study, in accordance to the NIH policy for multisite studies. The DSMB charter has been uploaded in the eIRB application.

9.4.2 Risk Assessment

Psychological Stress and Anxiety. Due to the time associated with conducting the assessments, some subjects may experience fatigue, anxiety, or stress. The Baseline Assessment and live police interactions may also produce these feelings. Subjects will be allowed to take breaks and stop at any time.

The study visits will be organized to involve breaks for the subject, and to allow the subject to rest between procedures. Experienced clinicians will always be available to help in efforts to reduce anxiety. Research staff working on the project all have experience working with adolescents and adults, and the PI and co-Investigators each have extensive experience working with individuals with ASD, and will therefore do everything possible to accommodate subjects.

Risk of Seizures and Migraines. There is a very low risk of seizures as a result of Virtual Reality technology, which is significantly increased for individuals with a history of seizures. There is also a low risk of migraines, which is significantly increased for individuals with a history of migraines. To reduce both of these risks we will screen all subjects for both a personal and family history of seizures and a personal history of migraines, and exclude any subject who

screens positive for either personal or family history of seizure activity of any type or personal history of any degree or migraines.

There is also some evidence that sleep deprivation and recent alcohol use may increase risk for seizure activity during use of Virtual Reality or other technologies. Therefore, we will encourage participants to reschedule in the event of night-before sleep deprivation or recent alcohol use, to avoid testing on days with either of these risks present. Finally, there is some evidence that extended playing time is associated with increased seizure risk. Therefore, we include required breaks between trials in the Virtual Reality intervention, with approximately 20 minutes of VR and 20 to 25 minutes of break time during the 45 minute VR intervention condition.

Risk of Nausea and Eye Strain. Use of Virtual Reality technology can be associated with nausea or eye strain. To reduce this risk, we include required breaks between the VR trials, as described above. The experimenters will also ask the subjects how they are feeling in between each trial. Finally, the researcher will be aware of the potential for nausea and eye strain and will observe the subject for signs of potential nausea and/or eye strain, including covering the eyes, putting one's head down into their hands, holding one's head or stomach, etc. In cases where these potential indicators are observed, the experimenter will specifically ask how the subject is feeling and whether or not they are experiencing symptoms of nausea, eye strain, headache, or stomach pain or discomfort. If subjects report experiencing nausea or eye strain then the sessions will be stopped, in order to reduce risk of more serious adverse events such as migraines or seizures.

Risk of Musculoskeletal Injury. Use of virtual reality technology has potential to result in musculoskeletal injury. Specifically, as a result of differences in the virtual reality scene world and the real world, subjects may move in ways that do not match the real world with the risk of bumping into real world objects or falling. To reduce this risk, the Virtual Reality Police Intervention platform does not allow for "walking" within any of the virtual reality scenes. Instead, even if the subject moves forward, backward, or to the side, the VR environment does not change. As a result, movement of subjects is both discouraged and significantly reduced as a result of the virtual environment. However, movements do occur, and subjects are able to "rotate" / "spin around" and look upwards and downwards within the virtual environment. To further reduce the risk of musculoskeletal injury, subjects will use Virtual Reality in a central position of a room which is more than sufficient for the types of smaller-scale movements which are generally observed during this particular Virtual Reality Police Interaction training module. Furthermore, the experimenter will always be in the room with subject, and will monitor the subject's movement within the room and intervene if at any time there is potential for the subject to move to a location where an injury could occur, such as a wall or piece of furniture.

Sensorimotor Adaptations which Temporarily Affect Real World. Use of virtual reality technology has potential to result in sensorimotor adaptations (e.g., eye-hand coordination) which may result in a brief period of disorientation and risk for musculoskeletal injury. Specifically, as a result of differences in the virtual reality scene world and the real world, subjects may have briefly altered sense of their sensorimotor functioning in the real world. To reduce the risk of injury as a result of any potential sensorimotor adaptations, we will implement

a brief post-intervention rest period during which the subject is encouraged to both sit and rest and then stand up and walk around in a safe open room space with the experimenter present until any potential sensorimotor adaptations have reversed to normal.

Transmitted Diseases from Poor Hygiene. Head-mounted immersive virtual reality requires reuse of the same headset, earphones, and iPhone across subjects. As a result, there is risk of diseases being transmitted from one subject to another as a result of poor hygiene. To reduce the risk of disease transmission, the experimenters will wipe down all components of the physical setup using alcohol disinfectant wipes after each subject, as well as immediately prior to each new subject.

Breach of Confidentiality. To minimize this risk, all research records will be kept confidential and all research information will be associated with codes and not personal identifiers. The investigators will not be able to identify subjects' identities while working with the database created for this study.

Risk of Audio and video recording: There is the possibility that participants' audio-video recordings might be seen by someone outside of the study team. However, recordings will be kept on password-protected computers and DVDs/tapes will be kept in locked cabinets only accessible by the study team.

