5.2 Intervention: Virtual Reality Sessions

Each subject assigned to the PSM intervention will undergo three sessions over an approximately six week period (at least 24 hours between sessions). At the beginning of each session, research personnel will preview the VR session experience with the subject and a parent or caregiver as appropriate. The VR experience preparation will include screening of subject's health status and adjustment of the headset to fit the subject. The VR session will consist of multiple scenes in which the subject is approached and engaged by police officers in the virtual environment. Some police officer avatars in the virtual environment will be wearing facemasks to accurately reflect real-world masking behaviors in Cycle B. VR scenes will be presented via the Floreo application downloaded onto an iPhone worn by the participant in a lightweight, inexpensive VR headset. The VR interaction will be controlled and operated via linked iPad by a research staff member sitting with the subject at CAR in Cycle A, or via tele-administration in Cycle B. Subjects in the VR environment will receive live feedback from research staff members about police officer interaction expectations and safety in accordance with individual scene scripts and prompts. Each VR session should encompass four VR trials, each involving a non-identical police safety scene. The subject will take a break from the VR environment in between each trial.

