5.3 Control Conditions

5.3.1 Cycle A: Video Modeling

Subjects assigned to the comparison video modeling interaction will undergo three sessions over a period of six weeks that will consist of BE SAFE The Movie Curriculum Lessons 1-4 (https://besafethemovie.com/curriculum/). The BE SAFE The Movie Curriculum consists of video-based instruction on police officer interaction expectations and safety. These include Lesson 1: Laws Help us BE SAFE; 2: Law Enforcement Officers Help Us BE SAFE; 3: Uniforms and Safety Tools; 4: Stay Calm When You Meet the Police; within each of these lessons, participants will be shown videos, and then complete additional engaging video-based activities and short movie scenarios to video model. The lessons will be presented by research staff member sitting with the subject at CAR. Video observation, activities, and modeling sessions will be structured to correspond with VR session duration and total number. Participants in the video modeling interaction arm will be screened for subject health status in preparation for their sessions.

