5.6 Safety Evaluation

Immediately after completing each intervention session, research staff will ask subjects about any side effects experienced during the session. Research staff will also document the subject's overall perceived mood and emotional state.

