6.3.3 Safety Analysis

All subjects entered into the study at Visit 1 will be included in the safety analysis. The frequencies of AEs by type, body system, severity and relationship to study intervention type will be summarized. SAEs (if any) will be described in detail.

AE incidence will be summarized along with the corresponding exact binomial 95% two-sided confidence intervals.

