8 SAFETY MANAGEMENT

8.1 Clinical Adverse Events

Clinical adverse events (AEs) will be monitored throughout the study. The PI and the research team will work together to minimize minor adverse events. This will be accomplished through systematic assessment for adverse events through active clinical observation and post-session

questionnaires. If adverse events occur, we will solicit direct guidance and feedback from CHOP's IRB, and immediately implement safeguards to decrease or eliminate future risks. Minor AEs that are unrelated to study participation will be reported to CHOP's IRB and the NIH program officer in a quarterly report.

Safety research on Virtual Reality (VR) indicates that photosensitive seizures, headache, and vertigo are adverse events possibly related to VR use. Our study team will consider new onset seizure disorder, any seizure triggered during participation, and either headache or vertigo severe enough to result in an emergency room evaluation or hospitalization to be SAEs and respond accordingly.

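### In Cycle A, within-session symptom questions and targeted sign-watching are specified only for the VR arm, so adverse events may be recorded more often there through ascertainment alone

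*Combined protocol and SAP*

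**What the plan says.** **Both Cycle A arms.** Section 5.6 reads: "Immediately after completing each intervention session, research staff will ask subjects about any side effects experienced during the session". It also has staff document mood and emotional state. Section 8.1 describes, for the whole study, "systematic assessment for adverse events through active clinical observation" together with questionnaires after sessions. Section 9.4.1 adds a debrief after each session. Sections 5.2 and 5.3.1 give each arm a health screen beforehand, and 5.3.1 has a staff member sitting with the video-modeling subject.

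**VR arm only.** Under the nausea and eye-strain risk in section 9.4.2: "The experimenters will also ask the subjects how they are feeling in between each trial". The researcher also "will observe the subject for signs of potential nausea and/or eye strain" and, if signs appear, asks specifically about nausea, eye strain, headache and stomach symptoms. The sensorimotor paragraph of the same section adds a rest period after VR with the experimenter present. Section 5.5 gives capture of adverse effects as a reason for the optional recording of VR sessions. For video-modeling recordings it gives only comparison as the purpose.

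**Analysis.** Section 6.3.3 reads: "The frequencies of AEs by type, body system, severity and relationship to study intervention type will be summarized". AE incidence is to be given with exact binomial 95% intervals. Nothing is said about unequal elicitation or about the source of each event.

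**The concern.** Cycle A is randomized, and its video-modeling sessions are structured to match VR sessions in number and duration. Readers will therefore set the AE incidence of the two arms side by side, and that comparison is fair only if symptoms are sought in the same way.

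A mild, passing symptom is more likely to be noted when the subject is asked within minutes than when asked once at the end. If tiredness, headache or eye discomfort also arise during screen-based lessons (plausible, but not documented), VR could show more events than video modeling at the same true rate. Section 9.1.2 blinds the confederates and the coders. It does not list the staff who run the sessions and ask about symptoms.

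The overall objective in section 2 still includes a satisfactory safety profile, and Cycle A is the only part of the study with an active control. If the source of each event is not recorded, the effect of unequal questioning cannot be separated out afterwards.

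**Working it through.** The plan states no figure for AE ascertainment, so there is none to reproduce. The check counts scheduled prompts and then illustrates what the difference could do.

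**Inputs from the documents**
- VR trials per session: 4 (section 5.2: "Each VR session should encompass four VR trials, each involving a non-identical police safety scene"), which leaves 3 gaps between trials.
- VR sessions: 3 (section 5.2: "Each subject assigned to the PSM intervention will undergo three sessions over an approximately six week period").
- Video-modeling sessions: 3 (section 5.3.1: "Subjects assigned to the comparison video modeling interaction will undergo three sessions over a period of six weeks").
- Post-session question: 1 per session in each arm (section 5.6).

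**Prompt count per completing subject**
- VR: 3 × (3 + 1) = 12, of which 9 fall between trials.
- Video modeling: 3 × 1 = 3.
- Ratio 12/3 = 4. Of the VR prompts, 9/12 = 75% have no counterpart.

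The 12 applies when all trials are run. Section 9.4.2 stops a session on reported nausea or eye strain, so some VR subjects will have fewer.

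**Illustration 1: forgetting by session end.** Assume equal true risk p in each of 12 intervals (4 per session), full capture with VR, and recall probability r at session end for symptoms from the first three quarters of a video-modeling session. Neither p nor r is in the documents.
- Share of events missed with video modeling = 0.75 × (1 − r): 7.5% at r = 0.9, 22.5% at 0.7, 37.5% at 0.5.
- Recorded subject incidence: VR = 1 − (1 − p)^12; video modeling = 1 − (1 − p(0.25 + 0.75r))^12.

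| p | VR | r = 0.9 | r = 0.7 | r = 0.5 |
|---|---|---|---|---|
| 0.03 | 30.6% | 28.7% | 24.6% | 20.3% |
| 0.01 | 11.4% | 10.6% | 8.9% | 7.2% |

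If the 48 subjects are split 1:1 (an assumption), each arm has 24. The p = 0.03 row then differs by about 0.5, 1.4 and 2.5 subjects, and the p = 0.01 row by about 0.2, 0.6 and 1.0.

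**Illustration 2: repeated chances to detect.** Assume equal per-session symptom probability q, with each prompt detecting a symptom independently with probability s. Both values are again assumed.
- VR = 1 − (1 − q(1 − (1 − s)^4))^3; video modeling = 1 − (1 − qs)^3.
- At q = 0.10 and s = 0.7: VR = 1 − (1 − 0.10 × 0.9919)^3 = 26.9%; video modeling = 1 − (1 − 0.07)^3 = 19.6%. The ratio is 1.38, or about 6.5 against 4.7 of 24 subjects.
- Over q = 0.05 to 0.20 and s = 0.5 to 0.9, the ratio runs from 1.09 to 1.83.

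Both models push recorded VR incidence upward. Neither establishes how far.

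**The case against.** A reader might infer that video-modeling subjects have nothing but the post-session question. The documents do not support that: general observation, mood documentation, a health screen, a staff member alongside and debriefing all apply to them as well. None of these, however, is a scheduled symptom question during the session.

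A reader might also infer that the plan contains a formal between-arm AE comparison, which this would bias. Section 6.3.3 states no test, contrast or risk difference. Its phrase about relationship to intervention type can equally mean attribution of the event. That stands. Even so, AE incidence from a randomized two-arm cycle will be read by arm, and under the attribution reading VR-only prompts would still add to the count of VR-related events.

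Next, answers between trials are not expressly called AE data and serve subject welfare. That stands too, and it is why the size is unknown. But section 8.1 makes active observation an AE source, and a report that stops a session is unlikely to go unrecorded.

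Safety was already found acceptable under a separate protocol (section 2), and the primary and secondary endpoints contain no safety measure. The post-session question is asked at once, after a VR condition of about 45 minutes, so recall loss may be small. With 24 per arm, an exact 95% interval for 7/24 runs from 13% to 51%, far wider than the shifts illustrated. Any bias also runs against the product under test. These points keep the severity low; they do not remove the asymmetry.

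**Conclusion.** The point holds in a limited form. As written, Cycle A seeks symptoms more intensively with VR: 12 scheduled prompts against 3, plus targeted sign-watching and an observed rest period. AE frequencies and incidence under section 6.3.3 may be higher with VR for that reason alone.

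The prompt count follows directly from the documents for subjects who complete all trials. The effect on recorded incidence does not. The range of about 1.1 to 1.8 rests on assumed event and detection rates, on equal true risk, and on within-session reports being entered as AEs. The documents therefore support a statement that ascertainment is unequal, but not that safety results will be biased by a known amount. Only the interpretation of the safety data is affected. Severity is minor.

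**What to change.** - **Cycle A sessions:** have the staff member already sitting with video-modeling subjects ask the same how-are-you-feeling question, and use the same list of symptom signs, at three matching points in each session.
- **AE form:** add one field recording whether each event came from a within-session prompt, from observation or from the post-session question.
- **Section 6.3.3:** report all AEs by arm. In addition, tabulate by arm those elicited at the shared post-session question, as a supportive summary. This table should not replace the full one: used alone it would drop events observed during VR, and it would not fully restore symmetry, because VR subjects have already been asked up to three times that session.

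The cost is three brief interruptions per video lesson session, one extra form field and a sentence or two in section 6.3.3. The VR safety checks stay unchanged.

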3.1.3 Cycle B – Virtually-Based Efficacy Study

In the second year (after the completion of Cycle A), a virtually-based efficacy trial will be conducted by CHOP staff via videoconference. Subjects will be randomized to the VR intervention or to the treatment-as-usual condition (with stratification, see *Study Procedure*). Subjects in each condition will undergo a baseline assessment of police interaction skills via a novel pre-/post-intervention assessment and three sessions within an approximately six-week period. At the end of Visit 3, subjects' police interaction skills will be assessed. There will be an additional follow-up visit approximately 4 weeks post-training, for all participants, to readminister outcome measures, as an assessment of maintenance of learning.

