5.3.2 Cycle B: Treatment-as-usual

Subjects assigned to the control condition will not receive any training with PSM, but will engage with the software for their assessments, and will continue their other treatments as usual. Participants in the treatment-as-usual arm will be screened for subject health status in preparation for their sessions.

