7 STUDY INTERVENTION

7.1 Virtual Reality Intervention

Floreo's Police Safety Module (PSM) will offer a supervised VR experience for individuals with ASD. The software will be a downloadable application that provides a three-dimensional immersive scene for headset-compatible smartphones and a supervisory overview that can run on smartphones or tablets. The individual with ASD will use a smartphone capable of running the application with a dedicated headset providing the virtual environment.

- 1. Immersive story-based intervention. Floreo's PSM provides a fully realized and intricately detailed urban environment (Appendix figure 1), designed to engage the user in a virtual encounter with law enforcement officers. The immersive VR environment engages the individual with ASD as an actor in a virtual narrative, incorporating strategies from both story-based intervention and video modeling. The opportunity to enter a virtual environment is likely to be appealing for adolescents with ASD. A law enforcement officer with extensive experience working with individuals with autism spectrum disorder along with members of the Philadelphia Police Department have provided ongoing input into content and environment design for this product.
- 2. *Video modeling*. Floreo's PSM provides video modeling to an individual with ASD. The video demonstrates the approach and initial engagement efforts of various police officers in the virtual environment, from the perspective of the individual wearing the HMD (Appendix figure 2).
- 3. Supervised Learning Environment. Floreo's PSM allows a monitor to use a tablet or phone to supervise the individual's virtual world. The devices used by individual with ASD and the monitor are communicatively paired together over a network connection (Appendix figure 3).

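### Section 9.4.2 promises in-room supervision that remote Cycle B cannot provide, and its seizure and migraine exclusion does not match section 3.3.2

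*Combined protocol and SAP*

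**What the plan says.** **Supervision.** On musculoskeletal injury, section 9.4.2 states that "subjects will use Virtual Reality in a central position of a room which is more than sufficient for the types of smaller-scale movements" usually seen with this module. It adds that "the experimenter will always be in the room with subject" and will "intervene if at any time there is potential for the subject to move to a location where an injury could occur". For the rest period after VR, the subject is to sit, then stand and "walk around in a safe open room space with the experimenter present". None of these sentences names a cycle.

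Other sections separate the cycles. Section 3.1.3 says "a virtually-based efficacy trial will be conducted by CHOP staff via videoconference". Section 5.2 has the VR "operated via linked iPad by a research staff member sitting with the subject at CAR in Cycle A, or via tele-administration in Cycle B". Section 7.1 describes the two devices as "communicatively paired together over a network connection". Section 5.3.2 says Cycle B controls receive no training with the module "but will engage with the software for their assessments", and sections 5.4.1.2 and 5.4.2.2 describe recordings of participants in the headset at the baseline and post-treatment assessments.

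**Seizure and migraine history.** Section 9.4.2 says all subjects are screened, and that anyone positive for a personal or family history of seizures, or a personal history of migraine, is excluded. It mentions no review. Section 3.3.2, items 2 and 4, lists the same histories as exclusions but makes each one open to individual review by medical professionals at Floreo, the company that supplies the module. It gives no criteria for that review.

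**The concern.** A risk assessment tells the ethics board, the staff and the safety board which protections are in place. If a stated protection against falls and collisions cannot operate in one of the two cycles, those readers are misinformed about that cycle. Section 9.4.2 itself accepts that subjects move despite the design of the scenes, and offers the person in the room as a further layer. Section 9.4.1 likewise supports its statement that discomfort is well tolerated by pointing to a team member accompanying the subject throughout. Participants may be as young as 12 (3.3.1) and may include adults with diminished capacity (9.6.1).

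The second conflict bears on who is exposed to VR at all. Section 9.4.2 calls the seizure risk very low but markedly higher with a seizure history, and section 8.1 counts a seizure triggered during participation as a serious adverse event. Two sections that can give different answers for the same candidate leave screening staff without one rule.

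**Working it through.** No figure in the plan bears on this, so the check is a comparison of texts.

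**(a) Which safeguards survive the move to remote delivery**

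| Safeguard | Cycle A | Cycle B as written |
|---|---|---|
| Scenes do not respond to walking (9.4.2) | Applies | Applies |
| Breaks between trials (5.2, 9.4.2) | Applies | Applies |
| Asking how the subject feels between trials, watching for signs, stopping for nausea or eye strain (9.4.2) | Applies | Can be done over video |
| Central position in an adequate room (9.4.2) | Staff control the room | Rule stands, but no step confirms it remotely |
| Experimenter in the room, intervening before a collision (9.4.2) | Deliverable | Not deliverable |
| Experimenter present while the subject walks after VR (9.4.2) | Deliverable | Not in person |

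1. Section 5.2 seats staff beside the subject only in Cycle A. Staff on a video link are not in the room and cannot physically intervene. Presence in the rest period could loosely be read as presence on video; being in the room cannot.
2. No section names a substitute. Section 5.2 includes a parent or caregiver in the session preview where appropriate, but nothing requires that person to stay.
3. The gap is not confined to the intervention arm. Controls wear the headset for assessments (5.3.2, 5.4.1.2, 5.4.2.2), so it reaches every Cycle B subject, about 48 evaluable (3.2.2).

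**(b) One candidate, two sections**

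1. Take a person with a personal seizure history. Under 9.4.2 the answer is exclusion.
2. Under 3.3.2 the answer is exclusion subject to individual review, with the possible outcomes not stated.
3. If review can admit, the sections disagree about this person. If review only settles whether a reported event counts as a qualifying history, they nearly agree, though 9.4.2 still omits the review.
4. The first reading is the more natural, because case-by-case review has little purpose if every positive screen is excluded. It remains an inference.
5. The stated basis for concern is uneven: 9.4.2 gives raised risk for a history of seizures and for a history of migraines, but does not say this of family history.

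**The case against.** The strongest reply is that 9.4.2 reads as laboratory text not fully adapted to Cycle B. Its instructions on wiping down a shared headset also name no cycle. The main control on falls and collisions is the design of the scenes, which works in both cycles, and side effects are asked about after every intervention session (5.6). The protocol classes the procedures as minimal risk (8.2, 9.4.4), and section 2 reports acceptable safety under an earlier protocol. This reply stands as far as size goes, but it does not remove the conflict. Section 2 does not say whether the earlier study was remote or admitted these histories.

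On eligibility, it can fairly be said that both sections list the histories as exclusions, that 3.3.2 ends by barring anyone who does not meet the criteria, and that review may serve only to classify reported events. That is why confidence here is moderate.

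Three stronger inferences are tempting, and the documents do not support them:

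- *Cycle B subjects are unprotected.* Most safeguards in 9.4.2 carry over, as the table shows.
- *Cycle B alone lacks an emergency procedure.* Sections 8.1 and 8.2 cover classification and reporting of events. Neither sets out an emergency response for Cycle A either, although remoteness makes the absence matter more in Cycle B.
- *People with a seizure history will be enrolled.* Section 3.3.2 does not say so.

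**Conclusion.** Two text conflicts stand, and both should be fixed.

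(a) High confidence. The in-room supervision and physical intervention stated in 9.4.2 cannot be delivered in Cycle B, and rest-period presence cannot be delivered in person. What is lost is narrow: someone on hand to intervene, and a check that the remote space is suitable.

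(b) Moderate confidence. 9.4.2 states an absolute exclusion where 3.3.2 allows review. The conflict depends on the natural but unstated reading that review can admit.

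A reader might rate this as a must-fix by pointing to how often headsets are worn remotely. Such a count measures exposure, not risk, and training sessions and assessments held at the same visit would be counted separately. The documents give no harm rate and no number admitted on review. Endpoints, analysis and power are unaffected.

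The conclusion concerns the written plan, not what staff do in practice. The Cycle B consent forms (9.6) and the safety board charter (9.4.1) were not available and may hold further safeguards; the protocol text would still need to agree with itself.

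**What to change.** (a) In 9.4.2, limit the in-room and rest-period presence sentences to Cycle A. For Cycle B, require staff to confirm on video that the subject has a cleared central space before the headset goes on. Add a remote stop and emergency-contact step that also covers the rest period. The cost is a short check at each remote visit. Asking for a responsible adult on site would be a further design choice with a scheduling burden, not something the correction requires.

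(b) State one rule in 3.3.2, 9.4.2 and the screening interview. Either make the exclusion categorical, as 9.4.2 now reads, or keep the review, write its criteria into 3.3.2 and correct 9.4.2 to match. Which rule to keep is the sponsor's choice. A categorical rule may cost a few eligible subjects; keeping the review costs only the drafting of criteria.

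Both changes fit in one protocol amendment, with matching consent and screening wording.
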